7.3 Endpoints

Primary endpoint:

The following endpoints will address the primary objective (concerning Saxenda® only):

BMI and comorbidities:

- Number of patients with Body Mass Index (BMI)≥30 kg/m² (measured less than 6 months before date of first prescription).
- Number of patients with 27 kg/m² ≤BMI<30 kg/m² (measured less than 6 months before date of first prescription) and
 - ≥1 relevant comorbidity registered:
 - Dysglycaemia (T2DM or prediabetes), hypertension, dyslipidaemia, and/or obstructive sleep apnoea.
 - o No relevant comorbidities (described above) registered.
- Number of patients with BMI<27 kg/m² (measured less than 6 months before date of first prescription).
- Number of patients with BMI not measured within 6 months before date of first prescription.

 Protocol
 Date:
 23 November 2015
 Novo Nordisk

 Study ID: NN8022-4241
 Version:
 5.0

 UTN: U1111-1185-3661
 Status:
 Final

 EU PAS No.:
 CONFIDENTIAL
 Page:
 17 of 53

Stopping rule:

- Number of patients with at least 5% weight loss (measured 16-24 weeks after first prescription date) and continuing treatment.
- Number of patients with less than 5% weight loss (measured 16-24 weeks after first prescription date) and continuing treatment.
- Mean weight loss (measured 16-24 weeks after first prescription date) in patients not treated according to stopping rule.

Secondary endpoint:

The following endpoint will be used to address the first secondary objective (concerning Victoza[®] only):

- Number of patients with Victoza[®] prescriptions fulfilling at least one of the following criteria:
 - 1. Dose information of 3.0 mg per day, or
 - 2. Indication of weight management.

The following endpoints will be used to address the second secondary objective (concerning Saxenda® only):

- Adherence to dose escalation according to label:
 - o Number of patients who have reached a dose of 3.0 mg within 4-12 weeks after first prescription date.
- Concomitant medication with of other GLP-1 receptor agonists:
 - Number of Saxenda[®] patients with other GLP-1 receptor agonists prescribed during continued treatment with Saxenda[®] (continued treatment is defined as no gaps between prescriptions of more than 90 days, identified by examining repeat prescription dates).
- Duration of treatment with Saxenda®:
 - o Number of patients with a treatment duration of:

Protocol		Date:	23 November 2015	Novo Nordisk
Study ID: NN8022-4241		Version:	5.0	
UTN: U1111-1185-3661		Status:	Final	

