8.1.3 Treatment of patients

Patients will be treated with commercially available Saxenda® or Victoza® according to routine clinical practice at the discretion of the treating physician. Saxenda® and Victoza® both contain the

Protocol		Date:	23 November 2015	Novo Nordisk
Study ID: NN8022-4241		Version:	5.0	
UTN: U1111-1185-3661		Status:	Final	
FILPAS No.	CONFIDENTIAL	Page.	21 of 53	

active substance liraglutide - a long-acting GLP-1 analogue, and are both administered subcutaneously by injection. The approved posology for Saxenda[®] is a starting dose of 0.6 mg daily, which should be increased to 3.0 mg daily in increments of 0.6 mg with at least one week intervals to improve gastrointestinal tolerability. For Victoza[®], the approved posology is a starting dose of 0.6 mg daily, which should be increased to 1.2 mg after at least one week; based on glycaemic response, the daily dose can be increased from 1.2 mg to 1.8 mg after at least one week.

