8.2.6 Flowchart

The data collection period for Saxenda[®]/Victoza[®] will be the interval between the launch date of Saxenda[®] to the index date of the pilot or full study, respectively. Table 1 and Table 2 show the data to be collected respectively for Saxenda[®] and Victoza[®] patients at different time points in relation to initiation of treatment. Data collection will encompass the following treatment periods for Saxenda[®]: (1) a time frame of 6 months prior to treatment initiation, (2) treatment initiation, (3) 4-12 weeks post treatment initiation, (4) 16-24 weeks post treatment initiation, and also (5) throughout the entire treatment period. Data collection will encompass the following treatment periods for Victoza[®]: (1) treatment initiation, and (2) throughout the entire treatment period.

Protocol	UTN: U1111-1185-3661	Date:	23 November 2015	Status:	Final	Novo Nordisk
Study ID: NN8022-4241	EU PAS No.:	Version:	5.0	Page:	23 of 53	

Table 1 - Saxenda® patients¹

Weeks in relation to initiation of treatment/time of first prescription	Prior to treatment initiation	0	4 – 12 weeks	16 – 24 weeks	Throughout the treatment period ²
Visit window			+4 weeks	+4 weeks	
Demography ³		X			
Co-morbidities ⁴	X				
Body Weight		X^5		X^6	
Adult height	X				
BMI		X^5			
Brand name		X			
Indication prescribed		X			
Target dose prescribed		X			
Current dose ⁷			X	X	
Treatment start date		X			
Treatment stop date					X
Concomitant medication with GLP-1					
receptor agonists					X
(Brand name and start date)					

- 1) Inclusion criteria must be fulfilled (incl. obtained informed consent) before data extraction is performed
- 2) Censoring at 24 months after launch
- 3) Sex, age
- 4) Diagnosis of or treatment of pre-diabetes, type 2 diabetes mellitus (T2DM), hypertension, dyslipidaemia and/or obstructive sleep apnoea.
- 5) Latest recording within 6 months before first prescription of Saxenda®
- 6) If not available the earliest subsequent body weight and date of measurement should be recorded
- 7) If treatment discontinuation occurs prior to/between the specified time points, the dose of Saxenda® at time of treatment discontinuation should be recorded.

Protocol		Date:	23 November 2015	Novo Nordisk
Study ID: NN8022-4241		Version:	5.0	
UTN: U1111-1185-3661		Status:	Final	
EU PAS No.:	CONFIDENTIAL	Page:	24 of 53	

Table 2 - Victoza® patients¹

Weeks in relation to initiation of treatment/time of first prescription	0	Throughout the treatment period ²

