- HbA1c 5.7-6.4% (both inclusive)

T2DM:

- FPG \geq 126 mg/dL (7.0 mmol/L) and/or
- 2 hour post-challenge (during an OGTT) plasma glucose ≥ 200 mg/dL (11.1 mmol/L) and/or
- HbA1c > 6.5%
- O Diagnosis of obstructive sleep apnoea may be based on treatment with continuous positive airway pressure (CPAP) device.
- Concomitant medication with other GLP-1 receptor agonists (brand name and start date).
- Dose at 4-12 weeks and 16-24 weeks post initiation of treatment
- Body weight at 16-24 weeks post initiation of treatment. If body weight is not available within this interval, the earliest subsequent body weight and date of measurement should be recorded

Victoza® initators only:

• Dose throughout the treatment period

 Protocol
 Date:
 23 November 2015
 Novo Nordisk

 Study ID: NN8022-4241
 Version:
 5.0

 UTN: U1111-1185-3661
 Status:
 Final

 EU PAS No.:
 Page:
 26 of 53

Prescription outside label

Prescription outside label will be categorised as follows:

Saxenda® patients:

- BMI<27 kg/m² within 6 months before date of first prescription
- 27 kg/m² ≤BMI < 30 kg/m² within 6 months before date of first prescription and no relevant comorbidities registered (dysglycaemia [T2DM or prediabetes], hypertension, dyslipidaemia, and/or obstructive sleep apnoea)
- BMI not measured within 6 months before date of first prescription
- Non-adherence to dose escalation according to SmPC (i.e., daily dose of 3.0 mg not reached within 4-12 weeks post initiation of treatment)
- Non-adherence to stopping rule (i.e., less than 5% weight loss after 16-24 weeks on Saxenda[®] 3.0 mg and still on continued treatment)
- Concomitant medication with other GLP-1 receptor agonists

Victoza® patients:

- Dose of 3.0 mg per day
- Prescribed indication of weight management

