Saxenda® patients only:

- Comorbidities:
 - Dysglycaemia (T2DM or prediabetes), hypertension, dyslipidaemia, and/or obstructive sleep apnoea (number and proportion)
- Dose at 4-12 weeks and 16-24 weeks post initiation of treatment (mean, standard deviation)
- Duration of treatment (or ongoing treatment) (mean, standard deviation, median, first and third quartiles and range; number and proportion for treatment completion: completed treatment or ongoing treatment)

Victoza® patients only:

- Increase in Victoza® dose to 3.0 mg/day (number and proportion)
- Prescription of Victoza® for weight management (number and proportion)

Prescription outside label:

Descriptive statistics for the following:

Saxenda® patients:

- BMI<27 kg/m² (number and proportion)
- 27 kg/m²≤BMI<30 kg/m² and no relevant comorbidities registered (dysglycaemia (T2DM or prediabetes), hypertension, dyslipidaemia, and/or obstructive sleep apnoea) (number and proportion)
- BMI not measured within 6 months before date of first prescription (number and proportion)
- Non-adherence to dose escalation according to label (i.e., 3.0 mg not reached within 4-12 weeks after date of first prescription) (number and proportion)
- Non-adherence to stopping rule (i.e., less than 5% weight loss after 16-24 weeks on Saxenda® 3.0 mg and still on continued treatment) (number and proportion)

Protocol		Date:	23 November 2015	Novo Nordisk
Study ID: NN8022-4241		Version:	5.0	
UTN: U1111-1185-3661		Status:	Final	
EU PAS No.:	CONFIDENTIAL	Page:	31 of 53	

• Concomitant medication with other GLP-1 receptor agonists (brand name) (number and proportion)

Victoza® patients:

- Dose information of 3.0 mg per day (number and proportion)
- Prescribed indication of weight management (number and proportion)

All analyses will be performed using SAS 9.2 (or higher) statistical software (SAS Institute Inc., Cary, North Carolina, USA). Programs, logs, and output will be reviewed for accuracy according to relevant standard operating procedures.

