- Adherence to dose escalation according to label:
 - o Number of patients who have reached a dose of 3.0 mg within 12 weeks after first prescription date
- Concomitant medication use of other GLP-1 receptor agonists:
 - o Number of Saxenda[®] patients with other GLP-1 receptor agonists prescribed during continued treatment with Saxenda[®] (continued treatment is defined as no gaps between prescriptions of more than 90 days, identified by examining repeat prescription dates)
- Duration of treatment with Saxenda[®]:

Protocol		Date:	23 November 2015	Novo Nordisk
Study ID: NN8022-4241		Version:	5.0	
UTN: U1111-1185-3661		Status:	Final	
EU PAS No.:	CONFIDENTIAL	Page:	33 of 53	

- Number of patients with a treatment duration of:
 - 0-3, 4-6 months, or ongoing (current patients), with continued treatment defined as no gaps between prescriptions of more than 90 days, identified by examining repeat prescription dates.

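### As written, the dose-escalation category counts patients who stop before reaching 3.0 mg as prescribed outside label, and the planned dose data will almost always miss escalation faster than the quoted minimum interval

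*Protocol*

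**What the plan says.** Section 8.1.3 describes the Saxenda posology. Patients begin on 0.6 mg a day. On the later steps the text reads "which should be increased to 3.0 mg daily in increments of 0.6 mg with at least one week intervals".

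Section 7.3 sets the matching secondary endpoint: "Number of patients who have reached a dose of 3.0 mg within 4-12 weeks after first prescription date". Sections 8.3 and 8.7.2 turn it into an outside-label category. Section 8.3 has "daily dose of 3.0 mg not reached within 4-12 weeks post initiation of treatment", attributed to the SmPC. Section 8.7.2 has "Non-adherence to dose escalation according to label (i.e., 3.0 mg not reached within 4-12 weeks after date of first prescription", reported as a number and proportion. Section 8.7.2 also names the proportion of prescriptions outside label as the main analysis and says that each form will be described.

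The Saxenda dose data listed in section 8.3 are "Dose at 4-12 weeks and 16-24 weeks post initiation of treatment". Table 1 in section 8.2.6 puts a +4 week visit window on both readings, and its footnote 7 reads "If treatment discontinuation occurs prior to/between the specified time points, the dose of" Saxenda at that moment is to be recorded. Treatment stop dates and repeat prescription dates are collected. Dates of dose steps are not listed.

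Section 8.7.1 analyses all recruited patients, and section 8.7 bases categorical proportions on non-missing data. The pilot endpoint in section 8.7.3 is "Number of patients who have reached a dose of 3.0 mg within 12 weeks after first prescription date".

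**The concern.** The category is presented as departure from the label, but two things in the plan separate it from the posology that the plan quotes.

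First, a patient who stops treatment during titration has not reached 3.0 mg. Footnote 7 gives that patient a dose value, the all-patient analysis set keeps the patient in, and no separate category takes the patient out. Stopping early is thereby counted as prescribing outside label, whatever the prescriber did.

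Second, the one interval that section 8.1.3 states is a minimum between steps. Nothing in the listed Saxenda data shows when a step was taken, so a breach of that interval leaves almost no trace.

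The study is an EMA-requested commitment under the risk management plan, and this category feeds its main analysis. A figure that mixes early stopping with titration practice, and is nearly blind to rapid escalation, could mislead on both.

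**Working it through.** **Inputs.** Start 0.6 mg, increment 0.6 mg, target 3.0 mg, interval at least 1 week (section 8.1.3). Window 4-12 weeks (sections 7.3, 8.3 and 8.7.2). Dose readings at 4-12 and 16-24 weeks, each +4 weeks (Table 1). 150 Saxenda patients in the full study (section 8.2.1). The protocol gives no discontinuation or non-adherence rates, so those below are assumptions.

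**1. Reproducing the window.** Steps = (3.0 - 0.6)/0.6 = 4. At one week or more per step, the earliest week for 3.0 mg is 4 x 1 = 4, which matches the lower limit. Twelve weeks corresponds to a mean interval of 12/4 = 3 weeks. Section 8.1.3 gives no maximum interval, so the upper limit cannot be derived from it.

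**2. Early stoppers who keep exactly to weekly steps.** Dose at stopping = 0.6 + 0.6 x (weeks completed):

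| Stop at week | Dose recorded (mg) | Category as written |
|---|---|---|
| 1 | 1.2 | outside label |
| 2 | 1.8 | outside label |
| 3 | 2.4 | outside label |

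None of them could have been at 3.0 mg yet under the quoted intervals.

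**3. Size of the inflation.** Let d be the fraction who stop before 3.0 mg and q the non-adherence among those still treated. Reported proportion = d + (1 - d)q. Inflation over q = d + (1 - d)q - q = d(1 - q).

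| d (assumed) | q (assumed) | Reported | Inflation |
|---|---|---|---|
| 10% | 0% | 10% | 10 points |
| 10% | 20% | 28% | 8 points |
| 30% | 0% | 30% | 30 points |
| 30% | 20% | 44% | 24 points |

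For 150 patients, the 28% row is 15 stoppers plus 20% of the other 135 (27), so 42 in all. The 44% row is 45 stoppers plus 20% of 105 (21), so 66.

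**4. Fast escalation.** At 0.25, 0.5 or 0.75 weeks per step, 3.0 mg is reached at week 1, 2 or 3. The reading at 4-12 weeks is 3.0 mg in each case, the same as for a patient who took one week per step. Read literally, the 4-week lower limit would exclude these patients, but the date of reaching 3.0 mg is not collected, so the limit cannot be applied. The exception is a patient who stops before week 4 while already on 3.0 mg: footnote 7 and the stop date would reveal that case.

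**5. Slow escalation and the windows.** At 3.5, 4 or 5 weeks per step, 3.0 mg is reached at week 14, 16 or 20. All three respect the quoted minimum interval, and all miss week 12. With the +4 weeks of Table 1, a dose taken as late as week 16 may fill the 4-12 week field. The patient stepping every 3.5 weeks then reads 2.4 mg at week 12 but 3.0 mg at week 16. Conversely, a patient stepping every 1.5 weeks reads 1.8 mg at week 4 and reaches 3.0 mg at week 6, so one reading early in the window can suggest a miss that did not occur.

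**The case against.** The best case for the plan has five parts.

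- **The posology also sets a destination.** Section 8.1.3 says that the dose should rise to 3.0 mg, so not reaching it is worth reporting, and a record review needs some finite cut-off. This stands. A reader might infer that the 12-week limit is wrong, or that every slow escalator is a false violation. The documents do not support that: section 8.3 attributes the rule to the SmPC, which is not reproduced, and a summary that is silent on a maximum does not show that the label has none.
- **Footnote 7 only asks for a dose to be recorded, and handling of discontinuers may be left to the SAP.** This stands in part. A SAP could add a denominator rule, but the protocol already fixes the category and the analysis set without one, and a SAP cannot recover step dates that were never abstracted.
- **Pilot and full study barely differ.** A reader might infer two different endpoints from the two wordings. They differ only in the 4-week lower limit, which cannot be applied, so in practice the counts would be nearly the same. The wordings still need aligning with each other and with the +4 weeks.
- **The component is visible.** It is one of six Saxenda categories, each described separately in a study without hypothesis tests. A reader might infer that the endpoint or the outside-label total mostly measures early stopping and slow titration. The protocol gives no rates from which to say so.
- **Step dates may be missing from routine records.** Section 8.9 warns that records may be incomplete and often lack information on actual use. This stands, and it limits what extra abstraction can deliver.

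**Conclusion.** The point holds in a limited form. As the protocol is written, patients who stop before reaching 3.0 mg are counted as prescribed outside label, including those who could not yet have reached it under the quoted posology. The inflation is d(1 - q), not d: 8 to 30 points for d of 10-30% and q of 0-20%. Both ranges are assumptions, and the direction is upward whenever d is above 0 and q below 1.

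Escalation faster than the quoted minimum interval is almost always missed. A reader might infer that it can never be detected, but the early stopper already on 3.0 mg is an exception.

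The 12-week limit is unsourced in section 8.1.3, which calls for reconciliation and does not show that the limit is wrong.

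**What to change.** 1. Report patients who discontinued before reaching 3.0 mg as their own category, using the stop dates already planned. Give the escalation proportion among patients still on treatment at the end of the window. Use footnote 7 doses descriptively only. This changes wording in sections 7.3, 8.3, 8.7.2 and 8.7.3 and needs no new data.
2. Abstract the date on which 3.0 mg was first prescribed, and the dates of dose steps where the record has them. This costs some added CRF fields and abstraction time, and the records will be incomplete, so the number with usable dates should be shown. It has to be decided before abstraction starts.
3. Reconcile sections 7.3, 8.1.3, 8.3, 8.7.2, 8.7.3 and Table 1 on a single window, including whether a dose recorded in the +4 weeks counts, and state the label source for the 12-week limit. Which titration rule defines adherence is for the sponsor to settle from the label. This review does not choose one.

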8.7 Data analysis

All data analysis will be performed by

As this is a descriptive study that will investigate in-market utilisation of liraglutide, no formal statistical testing will be conducted.

Characteristics of study participants will be reported as mean, standard deviation, median, first and third quartiles and range for continuous variables and as number and proportion of patients with observed (non-missing) data for categorical variables. Study participation will be presented, including number of sites approached for the study and response rate, by specialty, and number of patients approached, response rates, and reasons for refusal. Characteristics of the participating sites and patients will be presented, stratified by country. The data may also be evaluated and presented for other meaningful subgroups of patients (e.g., by sex or age). Comparison between participants and non-participants will be made for sites and patients. Participating and non-participating sites will be compared on geographic location, area of primary practice, practice type, practice size and

Protocol		Date:	23 November 2015	Novo Nordisk
Study ID: NN8022-4241		Version:	5.0	
UTN: U1111-1185-3661		Status:	Final	
FILPAS No.	CONFIDENTIAL	Page.	29 of 53	

patient volume. Comparison of participating patients and the total population of patients treated with Saxenda[®] or Victoza[®] will be made, subject to data availability.

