8.7.2 Statistical methods

Details of the data analyses, along with table, listing and figure (TLF) templates, will be fully described in a Statistical Analysis Plan (SAP).

In brief, the descriptive analyses will present Saxenda[®] and Victoza[®] utilisation by indication. Results will be evaluated by site characteristics, including country and geographic region within country, to ascertain any patterns of prescribing by specific indication. The main analysis will be to estimate the proportion of prescriptions outside label among Saxenda[®] or Victoza[®] patients during the entire study period in the countries of interest. The proportion of each of the forms of prescription outside label will be described (see section on prescription outside label). Characteristics of patients prescribed Saxenda[®] or Victoza[®] according to the respective approved SmPCs will also be evaluated.

Analyses on the following will be conducted:

Site characteristics

Descriptive statistics will be provided for the following variables:

- Geographic location of physician site (number and proportion)
- Specialty or area of primary practice (e.g. GPs, cardiologists, endocrinologists (or other diabetes and obesity specialists), etc.) (number and proportion)
- Practice type (e.g. community hospital, academic/medical centre, office based, etc.) (number and proportion)
- Number of physicians who practice at site (mean, standard deviation, median, first and third quartiles and range)
- Patient volume (i.e. number of patients and estimated number of patients using Victoza[®] or Saxenda[®]) (mean, standard deviation, median, first and third quartiles and range)

Patient demographics, medical history, and other characteristics:

Descriptive statistics will be provided for the following variables:

- Age (mean and standard deviation; number and proportion for age categories)
- Sex (number and proportion)

Protocol		Date:	23 November 2015	Novo Nordisk
Study ID: NN8022-4241		Version:	5.0	
UTN: U1111-1185-3661		Status:	Final	
EU PAS No.:	CONFIDENTIAL	Page:	30 of 53	

Drug utilisation:

Descriptive statistics will be provided for the following variables:

Saxenda® or Victoza® patients:

- Brand name (number and proportion)
- Indication prescribed at treatment initiation (number and proportion)
- Target dose prescribed at treatment initiation (number and proportion for target dose categories: 3.0 mg/day (for Saxenda® patients) and 1.2 mg/day, 1.8 mg/day or 3.0 mg/day (for Victoza® patients)

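### The Saxenda outside-label list tests dose only on the low side, so a recorded dose above 3.0 mg/day has no dose category

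*Protocol*

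**What the plan says.** Section 8.3 of the protocol introduces its classification with "Prescription outside label will be categorised as follows" and then lists six Saxenda items:

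1. BMI below 27 kg/m².
2. BMI from 27 to below 30 kg/m² with no relevant comorbidity.
3. No BMI in the six months before the first prescription.
4. Failed dose escalation, defined as "daily dose of 3.0 mg not reached within 4-12 weeks post initiation of treatment".
5. Stopping rule not followed.
6. Another GLP-1 receptor agonist taken concomitantly.

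Section 8.7.2 repeats the six items and words the dose item as "3.0 mg not reached within 4-12 weeks after date of first prescription".

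The list feeds the headline result. Section 8.7.2 states: "The main analysis will be to estimate the proportion of prescriptions outside label". The same section says that the characteristics of patients prescribed either product "according to the respective approved SmPCs will also be evaluated".

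The posology in section 8.1.3 starts at 0.6 mg daily and rises in 0.6 mg steps to 3.0 mg daily. No higher dose is mentioned. Section 7.2 makes adherence to that posology the second secondary objective, and its dose endpoint in 7.3 counts patients who reached 3.0 mg in the 4-12 week window.

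Two dose displays are planned in 8.7.2. Target dose has a single Saxenda class ("number and proportion for target dose categories: 3.0 mg/day"). The doses in the two windows are summarised as "Dose at 4-12 weeks and 16-24 weeks post initiation of treatment (mean, standard deviation").

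**The concern.** A dose can depart from a posology in two directions, and the list looks in only one. A patient whose record shows, say, 3.6 mg/day is not being dosed as section 8.1.3 describes, yet no outside-label dose item applies. If nothing else flags the patient, the main analysis does not count that prescription as outside label.

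The study was set up to compare real-world liraglutide use with the labels, and one of its stated objectives concerns posology. As the list stands, the report could not state how many Saxenda patients were dosed above 3.0 mg/day, even if the answer were none. The list is written into the protocol as the classification to be used, so an analysis plan that follows it would inherit the gap.

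**Working it through.** The protocol states no figure that bears on this point, so there is nothing to reproduce. The check is to run doses through the written rule and then see whether another provision catches what the rule misses.

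**Dose item applied to a dose recorded at 4-12 weeks**

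| Recorded dose (mg/day) | Reached means at least 3.0 | Reached means exactly 3.0 |
|---|---|---|
| 1.8 | failed escalation | failed escalation |
| 2.4 | failed escalation | failed escalation |
| 3.0 | no dose item | no dose item |
| 3.6 | no dose item | failed escalation |
| 4.2 | no dose item | failed escalation |

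The middle column is the plain reading. On the exact reading the patient enters the outside-label total, but under a label that says the opposite of what happened. Neither column counts dosing above the posology. A patient at 3.0 mg at 4-12 weeks and 3.6 mg at 16-24 weeks is missed on both readings, because the item looks only at the earlier window.

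**Other provisions**

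- *Stopping-rule item (8.3).* It names 3.0 mg as a condition, but tests weight loss and continuation.
- *Concomitant GLP-1 item (8.3).* It might catch liraglutide above 3.0 mg taken by adding Victoza, if Victoza counts as another agent. It does not test the Saxenda dose.
- *Target-dose display (8.7.2).* A target above 3.0 mg lowers the share in the 3.0 mg/day class, but so does a target below it.
- *Window doses (8.7.2).* Suppose 3 of 150 patients are at 3.6 mg and 147 at 3.0 mg. The mean is 3.0 + (3 × 0.6)/150 = 3.012 mg. The SD is 0.6 × √[(3/150) × (147/150) × (150/149)] = 0.084 mg. Neither value would draw attention.
- *General rule in 8.7* ("mean, standard deviation, median, first and third quartiles and range for continuous variables"). Applied to dose, a range would show the highest value, but not how many patients had a high dose.
- *Data-entry checks (8.6).* They may query a high value, but they do not classify the patient.

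**Size per patient not flagged otherwise, plain reading**

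The protocol plans 150 Saxenda and 150 Victoza patients in the full study, and 50 Saxenda patients in the pilot (8.2.1).

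- Full-study Saxenda patients: 1/150 = 0.67 percentage points.
- Full-study plus pilot Saxenda patients: 1/(150 + 50) = 1/200 = 0.50 points.
- Both products pooled, full study: 1/(150 + 150) = 1/300 = 0.33 points.

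The protocol gives no frequency of such doses. As an assumption only, 0 to 3 such patients among 150 would lower the proportion by 0 to 3/150 = 2.0 points.

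**The case against.** The strongest reply is that this is a choice of scope. Section 6 is concerned with one liraglutide product being used for the other's indication, and the lists serve that concern. Nothing in the protocol suggests that Saxenda is prescribed above 3.0 mg/day. Section 8.1.3 gives 3.0 mg as the dose to increase to, without calling it a maximum, and the SmPC that would settle this is cited but not reproduced. These points stand. They are why the size may be zero and why treating a higher dose as outside the posology is an inference, though a natural one. They do not explain why a study with a posology objective tests one direction only.

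A second reply is that 8.7.2 evaluates within-label patients by the SmPCs, which should keep a patient above 3.0 mg out of that group. That is fair, but it does not put the patient in the outside-label group; the patient could end up in neither.

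A reader might also infer that every patient above 3.0 mg/day would be misclassified, or that the 7.3 dose endpoint is wrong. The documents do not support either. A patient at 3.6 mg has reached 3.0 mg, so the 7.3 count is correct as worded. A patient already outside label for another reason, such as no recent BMI, does not change the total. On the exact reading, a high dose at 4-12 weeks changes only the category.

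Finally, the layout of the target-dose table can be left to the analysis plan. The outside-label list cannot, because the protocol fixes it.

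**Conclusion.** The point holds as a minor gap in classification. The list has no item for a Saxenda dose above the end dose given in 8.1.3. On the plain reading, such a patient is left out of the outside-label proportion unless flagged for another reason. The cost is 0.67 percentage points per patient with 150 full-study Saxenda patients as the denominator, and less with a larger one. The total effect is unknown and may be zero.

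This rests on two assumptions: that reached means at least 3.0 mg, and that 3.0 mg is the upper end of the approved posology. The BMI, comorbidity and stopping-rule endpoints in 7.3 are untouched.

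**What to change.** Add one item to the Saxenda outside-label list in 8.3 and again in 8.7.2: recorded target dose, or dose at 4-12 or 16-24 weeks, above 3.0 mg/day, reported as number and proportion. All three doses are already collected (8.3 and Table 1), so no new data, sites or patients are needed.

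The cost is one extra table row. A high dose recorded only outside those time points would still be missed.
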